10.3 STATISTICAL ANALYSES

10.3.1 Analysis of the Primary Endpoints

Point estimate and its standard deviation and 95% confidence interval will be calculated for the PFS6 for HMP cohort and NHMP cohort, respectively. Kaplan-Meier estimates will be used to describe the PFS for each cohort. The log-rank test will be used to compare the PFS of two cohorts.

10.3.2 Analysis of the Secondary Endpoint(s)

The similar analyses will be performed for PFS at 12 months as those for PFS6. We will assess the relationship between the neoantigen burden in tumor prior to the treatment and the PFS using the proportional hazard model. The neoantigen burden and HMP status (HMP/NHMP) will be included in the model as the covariates, and their potential interaction will be assessed. Other important baseline prognostic factors will also be included in the model to adjust for the potential confounders. We will evaluate the relationship between the neoantigen burden in tumor prior to the treatment and the objective response using logistic regression with the neoantigen burden and HMP status as covariates. Linear mixed model will be used to examine the trajectory of the longitudinal measures of symptom burden quantified using the MDASI-Brain tumor module. Random intercept will be included to account for the within-subject correlation and HMP status will be included as a covariate.

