1.1.2 Secondary Objectives

- To determine the 1-year progression free survival rate and overall survival in IDH-mutant gliomas patients with and without HMP in response to nivolumab treatment.
- To determine whether the neoantigen burden in tumor prior to the treatment is correlated with treatment response.
- To longitudinally evaluate patient reported outcome measures using self-reported symptom severity and interference with daily activities using the MDASI-BT.

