1.2.3 Cancers with high mutation burden better respond to checkpoint inhibitors

Tumor mutation burden (TMB) can be affected by a variety of causes, including but not limited to the exposure to mutagens, such as TMZ, and deficient MMR. When TMB is high enough, it may be associated with an increased hyper sensitivity to the immune checkpoint inhibitors, potentially due to the expression of immune-reactive neo-antigens in the tumors. This concept has been proven in a variety of refractory cancers [21-23]. Many of the tumors that respond to immune checkpoint inhibitors have deficient mismatch repair (MMR) mechanisms, which leads to 10 to100 times as many somatic mutations as those with proficient MMR [24-26]. Moreover, findings that are consistent with immune response, such as lymphocyte infiltration was found in MMR deficient tumors [27, 28]. The connection between the presence of deficient MMR and better immune response was made, since the somatic mutation can be recognized by the immune system

[29]. There has also been an increasing body of evidence to suggest that the cancers exhibiting high TMB, such as bladder cancer, non-small cell lung cancer and melanoma, are responsive to check point inhibitors [30-32]. High mutation and neoantigen burden may also be associated with improved response to immune checkpoint inhibitor in gliomas[33]. Studies of GBM patients with biallelic mismatch repair deficiency (bMMRD), a cancer predisposition syndrome, demonstrated a high mutation burden in their tumors [33, 34]. In this study, authors have demonstrated that all high grade bMMRD tumors are hypermutant, harboring over 100 exon mutations averagely. In the neoantigen analysis, the mean neoantigen burden was seven to 16 times higher than those of immune responsive melanomas, lung cancers, and microsatellite-unstable GI cancers. The case report of a significant responses of recurrent multifocal GBM to nivolumab in two siblings who have bMMRD has provided appealing evidence to theory that checkpoint inhibitor can induce significant clinical responses.

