therapy. The primary outcome measure was overall survival (OS), and the secondary outcome included overall survival rate, progression-free survival (PFS), and objective response rate (ORR). The result was presented in May 2017. At the time of final analysis, 369 pts were randomized, where 182 received nivolumab and 165 received bevacizumab. At baseline, 40% patients received nivolumab and 43% of patients received bevacizumab required corticosteroids. The OS was 9.8 months with nivolumab and 10.0 months with bevacizumab, and the 12-mo OS rate was 42% in both arms. PFS medians were 1.5 months (nivolumab) and 3.5 months (bevacizumab). Among evaluable patients treated with nivolumab (n = 153) or bevacizumab (n = 156), ORRs were 8% (nivolumab) and 23% (bevacizumab); duration of response medians was 11.1 months (nivolumab) and 5.3 months (bevacizumab). Treatment-related AEs (TRAEs) occurred in 57% (nivolumab) and 58% (bevacizumab) of patients; the most common TRAEs ($\geq 10\%$ of patients in either arm; nivolumab vs bevacizumab) were fatigue (21% vs 14%) and hypertension (1% vs 22%). Grade 3–4 TRAEs were reported in 18% (nivolumab) and 15% (bevacizumab) of patients. Serious AEs (all causality) were reported in 46% (nivolumab) and 35% (bevacizumab) of patients; seizure (8% vs 6%) and malignant neoplasm progression (11% vs 7%) were the only serious AEs reported in $\geq 5\%$ of patients in either arm. AEs leading to discontinuation occurred in 10% (nivolumab) and 15% (bevacizumab) of patients. Unfortunately, the study did not meet its primary endpoint of improved overall survival over bevacizumab monotherapy. The ORR was lower in the nivolumab arm than the bevacizumab arm. However, the response with nivolumab was more durable. The safety profile of nivolumab was very consistent with what has been observed in other tumor types. [40]

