10.1.1.1 Sample Size Determination

A maximum of 29 patients with HMP IDH-mutant gliomas, and a maximum of 30 patients with NHMP IDH-mutant gliomas will be enrolled in this phase II trials. Under the design described previously and given the type I error rate of 0.05, we have 80% power to reject the null hypothesis PFS6 = 0.1 for the HMP cohort given the alternative hypothesis PFS6 = 0.3; and 80% power to reject the null hypothesis PFS6 = 0.19 for the NHMP cohort given the alternative hypothesis PFS6 = 0.39.

Up to 59 study patients who undergo at least 1 cycle (2 infusions of nivolumab) is required. As we take into account approximately 20% of screen failures/non-evaluable patients, the overall accrual ceiling is 70 study patients.

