10.2 POPULATIONS FOR ANALYSES

10.2.1 Evaluable for toxicity:

All patients will be evaluable for toxicity from the time of their first treatment with nivolumab.

10.2.2 Evaluable for objective response:

Only those patients who have measurable disease present at baseline, have received at least one cycle of therapy, and have had their disease re-evaluated will be considered evaluable for response. These patients will have their response classified according to the definitions stated below. (Note: Patients who exhibit objective disease progression prior to the end of cycle 1 will also be considered evaluable.)

10.2.3 Evaluable Non-Target Disease Response:

Patients who have lesions present at baseline that are evaluable but do not meet the definitions of measurable disease, have received at least one cycle of therapy, and have had their disease re-evaluated will be considered evaluable for non-target disease. The response assessment is based on the presence, absence, or unequivocal progression of the lesions.

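### The logistic model of response on neoantigen burden and HMP status has no sparse-data method; at an assumed 8% response rate it has about 5 responders and no finite HMP coefficient in about 1 trial in 6.

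*Combined protocol and SAP*

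**What the plan says.** One secondary objective in section 1.1.2 is "To determine whether the neoantigen burden in tumor prior to the treatment is correlated with treatment response". Section 10.3.2 gives it two analyses. The first is a proportional hazards model for PFS, with neoantigen burden, HMP status, their possible interaction and other prognostic factors. The second models "the objective response using logistic regression with the neoantigen burden and HMP status as covariates". Only two covariates belong to the second model; the interaction and the prognostic factors are stated for the PFS model.

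For the response model the plan gives no expected number of responders, no minimum number needed to fit it, no rule for separation, and no penalised or exact method.

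Section 10.1.1.1 sets the size: "A maximum of 29 patients with HMP IDH-mutant gliomas, and a maximum of 30 patients with NHMP IDH-mutant gliomas". Section 10.2.2 limits the response set further: "Only those patients who have measurable disease present at baseline, have received at least one cycle of therapy", and disease must also have been re-evaluated. Sections 10.1.1 and 10.3.4 allow the HMP cohort to end after 10 patients.

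Section 10 assumes no response rate. The only rate for nivolumab monotherapy in the documents is the background figure in section 1.2.4: "ORRs were 8% (nivolumab) and 23% (bevacizumab".

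**The concern.** Logistic regression draws its information from the smaller outcome group, here the responders. With about five, two problems arise in an ordinary maximum-likelihood fit.

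- **Separation.** If one cohort has no responder, the HMP log-odds ratio runs to infinity and the joint fit does not exist. The analyst must then choose after seeing the data: drop HMP status, change method, or report an unusable coefficient.
- **Small-sample bias.** Even when every coefficient is finite, maximum-likelihood log-odds ratios are biased away from zero. This affects the neoantigen coefficient directly and does not depend on separation.

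At stake is the credibility of one of the two analyses serving a secondary objective. The primary endpoint and the stopping rules are untouched.

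**Working it through.** **Inputs**
- Cohort maxima of 29 HMP and 30 NHMP (section 10.1.1.1). The plan's total reproduces: 29 + 30 = 59.
- Response rate p = 8% (section 1.2.4, recurrent glioblastoma, 153 evaluable patients). Using it here is an assumption. If 8% is 12/153, the exact 95% interval is 4.1% to 13.3%.
- HMP stage I rule: stop at 10 patients if 9 or more progress by 6 months (section 10.1.1). The exact two-stage calculation gives type I error 0.0471 and power 0.805, matching the stated 0.05 and 0.8.
- The share of patients with measurable disease is not given, so 59 is a ceiling.

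**Step 1: responders.** Expected number = 59 × 0.08 = 4.72, or 4.72 / 2 = 2.4 per covariate. From Binomial(59, 0.08), P(5 or fewer) = 67% and P(fewer than 10) = 98%. At p = 13.3%, P(fewer than 10) is still 75%.

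**Step 2: probability that a cohort has no responder.** With a common rate p, this is (1−p)^29 + (1−p)^30 − (1−p)^59. At 8%: 0.0891 + 0.0820 − 0.0073 = 0.164, about 1 in 6.

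| Common response rate | 29 + 30 | 24 + 24 (assumed evaluable) | 10 + 30 (HMP stops) |
|---|---|---|---|
| 8% | 16% | 25% | 48% |
| 10% | 9% | 15% | 38% |
| 12% | 5% | 9% | 29% |
| 15% | 2% | 4% | 20% |

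At 5% with 29 + 30 it is 39%. With unequal rates at 29 + 30, it is 31% for 12% HMP and 4% NHMP, and 9% for 16% and 8%.

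**Step 3: allowing for the HMP stopping rule.** P(stop) = P(at most 1 of 10 progression-free), which is 0.736 if HMP PFS6 is 0.1 and 0.149 if it is 0.3. Taking stopping as independent of response, at 8%:
- PFS6 0.3: 0.149 × 0.481 + 0.851 × 0.164 = 21%.
- PFS6 0.1: 0.736 × 0.481 + 0.264 × 0.164 = 40%.

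**Step 4: which coefficient is lost.** In 6,000 simulated trials per scenario (29 + 30, 8%), each fit was checked for complete or quasi-complete separation. The joint fit failed in 16–18%. The neoantigen coefficient itself had no finite estimate in 1–2% with no or moderate effect, 4% with skewed burden, and 6% with a strong effect (log-odds 2 per SD). The cohort that has responders usually still identifies it.

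**Step 5: bias when the fit converges.** This used 1,500 simulated trials per effect size, with 29 + 30 patients, 8% overall response, and an assumed correlation of 0.5 between HMP status and burden.

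| True log-odds per SD | Joint ML fit fails | ML mean, converged fits | Firth mean, all trials |
|---|---|---|---|
| 0.5 | 17% | 0.57 | 0.47 |
| 0.8 | 23% | 0.96 | 0.79 |

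The ML excess is 0.07 / 0.50, about 13–14%, and 0.16 / 0.80 = 20%. Firth was finite in every trial. In a separate simulation, also at correlation 0.5, with true log-odds 0.5, root mean squared error was 0.79 for ML and 0.61 for Firth. The bias figures depend on the assumed effect and correlation and show order of magnitude only.

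**The case against.** The 8% is background from another trial in recurrent glioblastoma. This trial enrols IDH-mutant glioma, and section 1.2.3 says: "High mutation and neoantigen burden may also be associated with improved response to immune checkpoint inhibitor in gliomas". At 15% with all 59 patients, the chance of an empty cohort is only about 2%. This stands, and the result is therefore stated as conditional, with a range. It does not remove the point, because the documents offer no other rate and evaluable numbers can only be lower than 59. If higher burden does raise response, responders also concentrate in the HMP cohort, which works against the fit.

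A reader might infer that the neoantigen analysis itself would have no estimate in about one trial in five. The documents do not support that. The objective concerns neoantigen burden, HMP status is the adjusting covariate, and it is mainly the HMP coefficient that diverges. Even for the joint fit, one in five is not what 8% of 59 gives. It needs a response rate near 7.3%, about 27 evaluable patients per cohort, early stopping, or a chosen correlation between HMP status and burden. Simulated joint failure at 29 + 30 was 16–19% at correlation 0.3, 19–22% at 0.5 and 21–29% at 0.7, and the plan gives no correlation.

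It is also fair that the bias is small beside the sampling error with five responders, that the PFS model will have far more events, and that the text does not name maximum likelihood, so a penalised fit would not contradict it. Exact logistic regression or a descriptive summary would be defensible too. None of this is a reason to leave the unpenalised default in place.

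**Conclusion.** The concern holds in a limited form. The response model is specified without any sparse-data method, and on the only rate available it would rest on about five responders. At a common 8% rate and full accrual, the HMP coefficient has no finite maximum-likelihood estimate in about 1 trial in 6; rates of 5% to 15% move this from 39% to 2%. The neoantigen estimate is lost in about 1–6% of trials. Otherwise it exists, but is biased away from zero by roughly 13–20% for assumed effects of 0.5 to 0.8 log-odds per SD.

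These sizes rest on the carried-over 8%, on up to 59 evaluable patients, and on assumed effect sizes and correlation. They do not show that the secondary objective cannot be addressed. This is a cheap improvement to one secondary analysis.

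**What to change.** Add one sentence to section 10.3.2: the logistic model for objective response will be fitted by Firth's penalised likelihood, with profile-penalised-likelihood confidence intervals, whatever the number of responders. State that the result is descriptive and that responder counts will be shown by cohort.

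This keeps the HMP and neoantigen estimates finite, removes most of the small-sample bias, and rules out a change of method after the data are seen. It adds no information: about 2 responders per covariate remain at the assumed rate, so intervals will be wide. The cost is that sentence, standard software, and slight shrinkage if responses turn out more frequent.

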10 STATISTICAL CONSIDERATIONS

10.1 STATISTICAL HYPOTHESIS

10.1.1 Primary Endpoint: PFS at 6 months

Hypothesis: The PFS6 for HMP cohort is 30% or better, and PFS6 for NHMP is 39% or better.

Simon's optimal two-stage design [57] will be used for conducting the trial for the HMP and NHMP cohorts independently. Specifically, for the HMP cohort, the null hypothesis is that the PFS6 is 0.1, and the alternative hypothesis is that the PFS6 is 0.3. The trial is carried out in two stages. In stage I, a total number of 10 patients is accrued. If 9 or more patients progressed by 6 months, the cohort will be terminated early; otherwise, additional 19 patients will be accrued in stage II, resulting in a total sample size of 29. Among these 29 patients, if 6 or more patients are progression-free at 6 months, we reject the null hypothesis and claim that the treatment is promising for patients with HMP IDH-mutant gliomas. The design controls the type I error rate at 0.05 and yields the power of 0.8.

For the NHMP cohort, the null hypothesis is that the PFS6 is 0.186, and the alternative hypothesis is that the PFS6 is 0.386. The trial is carried out in two stages. In stage I, a total number of 15 patients is accrued. If 3 or more patients are progression-free at 6 months, the cohort will be moved to stage II and additional 15 patients will be accrued in stage II, resulting in a total sample size of 30. Among these 30 patients, if 10 or more patients are progression-free at 6 months, we reject the null hypothesis and claim that the treatment is promising for patients with NHMP IDH-mutant gliomas. The design controls the type I error rate at 0.05 and yields the power of 0.8.

Rationale for the target PFS6 in HMP and NHMP cohorts:

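### The MDASI-BT trajectory model names no HMP-by-time term, so as written both cohorts share one symptom slope, which fits neither if their trends differ

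*Combined protocol and SAP*

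**What the plan says.** Section 1.1.2 sets the secondary objective: "To longitudinally evaluate patient reported outcome measures using self-reported symptom severity and interference with daily activities using the MDASI-BT". Section 10.3.2 gives the model: "Linear mixed model will be used to examine the trajectory of the longitudinal measures of symptom burden quantified using the MDASI-Brain tumor module". Its terms follow: a random intercept for the correlation within patients, and "HMP status will be included as a covariate". No HMP-by-time term, cohort-specific fit, random slope or form for time is stated.

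Earlier in the same paragraph, the proportional hazards model takes neoantigen burden and HMP status as covariates, "and their potential interaction will be assessed". So the plan names an interaction where it wants one.

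Section 10.3.2.1 adds summaries at each time point, error bars, individual patient profiles and a comparison of responders with non-responders. It does not say that any of these will be shown by cohort.

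**The concern.** The trial is run "for the HMP and NHMP cohorts independently", with its own PFS6 hypotheses for each cohort, and section 10.3.1 estimates PFS6 separately. Section 10.1.1 expects a glioblastoma-like course for HMP tumours and, in its rationale, an anaplastic-astrocytoma-like course for NHMP. Section 1.2.3 argues that tumours with a high mutation burden respond better to checkpoint inhibitors. None of this shows that symptom trends differ, but it gives no ground for assuming that they are parallel.

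A covariate without a time interaction makes that assumption. If it fails, the reported trend is wrong for both cohorts, and the HMP coefficient looks like a steady difference in symptom level when the cohorts are in fact diverging. Trajectory is what this model is meant to describe.

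**Working it through.** The plan gives no slope, SD or power for this model, so there is no stated figure to reproduce.

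**Algebra (no assumptions beyond the plain reading).** Write y = b0 + b1·time + b2·HMP + u + e, with u the random intercept. The expected HMP minus NHMP difference is b2 at every visit, so both cohorts have slope b1. Adding b3·HMP·time gives slope b1 for NHMP and b1 + b3 for HMP.

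**What the common slope estimates.** Inputs from the documents: at most 29 HMP and 30 NHMP patients (section 10.1.1.1), or 10 HMP if that cohort stops at stage I (section 3.1); forms at baseline and with imaging every 8 weeks (sections 3.4 and 3.5). Assumed: follow-up to week 48, linear time, equal baselines. With complete forms, the common slope is the patient-weighted mean of the cohort slopes, and b2 is the slope gap times the mean visit time. The mean of weeks 0, 8, …, 48 is 24 weeks.

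Slopes below are in points per 24 weeks. The simulations used 100 trials each, between-patient SD 1.5 and residual SD 1.0. The progression-limited column uses PFS6 of 0.30 and 0.386.

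| HMP/NHMP patients | True slopes | Arithmetic | Simulated, complete | Simulated, to about progression |
|---|---|---|---|---|
| 29/30 | 2 and 0 | 2 × 29/59 = 0.98 | 0.98 | 0.87 |
| 29/30 | +1 and −1 | 29/59 − 30/59 = −0.02 | −0.01 | −0.13 |
| 10/30 | 2 and 0 | 2 × 10/40 = 0.50 | 0.51 | 0.42 |
| 29/30 | 1 and 1 | 1 | 1.00 | 1.02 |

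In the first row, b2 should be 2 × 1 = 2.0 although the baselines are equal; the simulation gives 2.0 with complete forms and 1.0 when progression-limited. With HMP-by-time, the first row returns 1.98 and 0.00 (complete), or 2.01 and −0.01 (progression-limited).

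**Interval coverage over a range of gaps.** Assumed: random-intercept SD 1.2, residual SD 1.0, NHMP slope 0, forms until progression or week 48, exponential PFS. PFS6 values are from section 10.1.1: the nulls (0.10 and 0.186) and the alternatives (0.30 and 0.386). Each coverage range spans these two settings. The third and fourth columns give coverage by the common-slope 95% CI.

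| Gap per 8 weeks | Divergence at week 48 (gap × 6) | HMP slope covered | NHMP slope covered |
|---|---|---|---|
| 0.6 | 3.6 points | 0–4% | 1–36% |
| 0.3 | 1.8 points | 3–32% | 19–76% |
| 0.2 | 1.2 points | 24–59% | 47–86% |
| 0 | 0 | nominal | nominal |

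For scale, section 10.3.2.1 takes 2 points as the smallest meaningful change. These figures are approximate: at the 0.6 gap and null PFS6 values, two runs differing in visit details gave 1%/14% and 5%/33% (HMP/NHMP). If 6-monthly forms after progression are added, coverage is near 0% for both cohorts at gaps of 0.2 to 0.6. With HMP-by-time, coverage is about 92–98%.

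**The case against.** - **The restriction is read from silence.** Section 10.3.2 gives no model equation and does not exclude an HMP-by-time term. This stands, so the point is about the plan as written. The explicit interaction for the Cox model makes a main effect the natural reading, and the plan should settle it.
- **No document says that the symptom slopes differ.** Both cohorts target the same 20-point gain in PFS6, and the MDASI-BT objective does not ask for a cohort contrast. This stands: the harm is conditional. A 0.6 gap on its own would overstate the case, because it implies almost twice the 2-point threshold by week 48; hence the range.
- **The descriptive summaries would reveal divergence.** Only if shown by cohort, which section 10.3.2.1 does not say.
- **The interaction will be imprecise.** At a gap of 0.2 its standard error was 0.10 to 0.19, and English-only collection (sections 2.4 and 3.4) may reduce numbers. This stands, and it is a reason to estimate and not to test.

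Two stronger readings are tempting but unsupported. A reader might infer that the HMP coefficient is mostly the baseline gap; with zero baseline gap and slopes of 0.6 and 0 it still averaged about 0.36 to 1.9, so it absorbs the slope difference. A reader might also infer that earlier dropout in the faster-progressing cohort moves the common slope materially. At slopes of 0.6 and 0 it moved only from 0.23 to 0.26 between the two PFS6 settings. Sections 3.4 and 3.5 also continue forms every 6 months after treatment ends; with those included it was 0.29 to 0.30 in both settings, close to 0.6 × 29/59 = 0.295.

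**Conclusion.** The point holds as a cheap improvement. On the plain reading of section 10.3.2, both cohorts share one slope. That is algebra and does not depend on the simulations. If the trends differ, the common slope fits neither cohort, and the difference is reported as a spurious constant level difference. With equal slopes nothing is lost.

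The size depends on the slope gap, which the documents do not give. Coverage is poor for both cohorts at a gap of 0.6 in most settings run, and degraded to varying degrees at 0.2. These figures rest on the assumed SDs, linear time, equal baselines, no between-patient variation in slope, and dropout unrelated to symptom score given cohort.

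This is a secondary, descriptive endpoint. The PFS6 decision rules are unaffected.

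**What to change.** In section 10.3.2, state how time enters the model (linear or by visit), add the HMP-by-time interaction, and report each cohort's slope or visit means with a 95% CI. Say that the interaction is estimated and is not a powered test. Keep the pooled trend as a summary only.

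The cost is one model term, with no new patients or data. If the slopes are in fact equal, the cohort-specific standard errors are about 1.3 to 1.9 times the pooled one. For example, one simulation gave 0.059 and 0.069 against 0.044: ratios of 0.059/0.044 = 1.3 and 0.069/0.044 = 1.6.
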